The Research Design for this two-year SPIRE proposal to RR&D will comprise of testing for two cognitive-based training platforms for functional grasp and reach, respectively, on persons with cervical SCI (Fig 6A). The experimental set-ups developed at Stevens are modular and portable for conducting tests with Veterans having SCI at the James J. Peters VAMC. Testing of each platform represents a unique proposal aim. Execution of each aim will be done independently in each of the two years and similarly include: 1) adaptation of platforms for use with persons having SCI, 2) recruitment of five participants per year, 3) execution of a single 8-hour experimental session for each participant. Each session includes 3 hours for data collection, and the remaining time for preparation, rest, feeding, bathroom trips, and 90-minute washout of each experimental condition. Inclusion criteria for subjects include: 1) aged 18 to 65 years, post-SCI for more than 1 year, SCI between C1-T1 with hand weakness (2-4 out of 5 manual muscle test in intrinsic hand muscles of thumb or 5th digit).

[figure not shown]
The schedule for each 12-month aim: recruitment (months 1-6), refining protocols for SCI (months 1-6), SCI participant testing (months 6-9), data and statistical analysis (months 7-10) and dissemination via conference and paper writings and submissions (months 9-12). Recruitment will be done via IRB-approved flyers at local SCI clinics; study posting at clinicaltrials.gov; and communication with previous participants at our VAMC. Among the ten total subjects (five per aim), our enrollment plan includes at least three females, three Latinos, and three African Americans.

For each aim, the data analysis will involve *within-subject* comparisons across three conditions: (1) control with minimal-to-no cognitive feedback, (2) intermediate level of cognitive feedback, and (3) enhanced cognitive feedback. Enhanced feedback refers to addition of VR to glove feedback in Aim 1, and addition of vibration to visual feedback in Aim 2. For each condition, there will be three consecutive trial blocks (Fig 6B): 1) baseline – performing real-world task 25 times with no feedback before training, 2) training – performing training task 50 times with feedback specific to condition, 3) retention – performing real-world task 25 times with no feedback after training.

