Repeated-measures MANOVA will be utilized given the three condition groups and two or more performance metrics specific to each aim. Our previous analyses for Result #1 with able-bodied persons suggest that $n = 5$ is sufficient to show significant difference ($p < 0.05$) for MANOVA across three condition groups and two performance metrics (completion time, motion pathlength) at 90% power. **The primary hypothesis for each aim is that performance after training is significantly greater with enhanced feedback.** Both aims of this study will also capture 32-channel EEG recordings for exploratory analysis of coherence computations with select recordings of muscle EMG as in Fig 2C.

AIM 1: Investigate the effect of a “cognition” glove and virtual reality on grasp performance in SCI persons with partial hand paralysis.

The cognition glove protocol from Result #1 will be extended to include VR feedback to persons with SCI performing the grasp-and-place of a small cubic object.

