Challenges/Alternatives – There are two primary challenges to this project: 1) *For Aim 1, the ability of a person with SCI and compromised sensation to find and skillfully grasp the real object while viewing the virtual environment.* If the subject is overly challenged to grasp the real object, then virtual feedback will be provided in desktop mode. VR goggles will be removed, and the participant can see and grasp the real object directly while a virtual environment is projected onto a background monitor. We expect viewing the virtual environment peripherally will still have additive reinforcement effects [53]. 2) *For Aim 2, subjects with various levels of SCI and conditioning may experience more fatigue than others given a total of 300 trials per session.* For each Aim, condition 1 allows us to re-calibrate our procedures based on participant behavior and apparent onset of fatigue. Re-calibration includes longer rest periods and fewer trials. A pilot analysis in persons without SCI for a reach-to-touch task done in our lab [54] suggests MANOVA significant differences in performance (pathlength and contact accuracy) across two feedback conditions (reward, punishment) could be observed with only 40 trials per condition. For both Aims, fatigue will also be monitored from EMG recordings [55].

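### The form of the planned repeated-measures MANOVA is not named; in its doubly multivariate form, two metrics need all five participants complete, and the three or four listed metrics cannot be tested at all

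*Combined protocol and SAP*

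**What the plan says.** Section (c), Research Design and Methods, gives the only analysis method for the main comparison: "Repeated-measures MANOVA will be utilized given the three condition groups and two or more performance metrics". It states that "the data analysis will involve *within-subject* comparisons across three conditions": control, intermediate and enhanced feedback.

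Each aim has exactly five participants ("recruitment of five participants per year"), and all three conditions fall in one sitting ("execution of a single 8-hour experimental session for each participant"). Each condition has 25 baseline, 50 training and 25 retention trials.

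The sample-size statement takes five participants as enough at the 5% level, for "two performance metrics (completion time, motion pathlength) at 90% power". The AIM 1 section then lists four performance metrics, and the AIM 2 section lists three.

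The Challenges/Alternatives paragraph foresees, for Aim 2, that "subjects with various levels of SCI and conditioning may experience more fatigue than others given a total of 300 trials per session". Its response, for both aims, is to adjust rest and trial numbers after condition 1 and to monitor fatigue from EMG.

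The documents do not state the form of the MANOVA, whether the analysis unit is a participant mean or a single trial, which metrics enter the test, what happens when a condition is missed, or whether a participant would be replaced.

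**The concern.** A repeated-measures MANOVA can be built in several ways, and these behave very differently with five participants. The standard doubly multivariate version treats each participant as one long vector of metrics by conditions. It needs a complete vector from each participant, and more participants than contrast variables. The plan sits at that limit for two metrics and beyond it for three or four.

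Two things are at stake. First, if this version is meant, the main test for an aim may not exist, either because one session was cut short or because all listed metrics were entered. Second, because the version is not named, the choice between one that fails and one that runs would be made after the data are in hand.

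**Working it through.** **Inputs.** From section (c): n = 5 per aim, k = 3 conditions, p = 2 metrics in the power statement, α = 0.05, power 90%. From the AIM 1 and AIM 2 sections: p = 4 and p = 3 metrics listed. Not given: effect size, standard deviations, correlations, loss rate.

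**The plan's own figure.** The claim of 90% power at n = 5 cannot be reproduced, because no effect size, standard deviation or correlation is stated. The checks below show what each form would require.

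**Doubly multivariate form.** The number of contrast variables is q = p(k − 1). The test is Hotelling's T² with F on (q, n − q) degrees of freedom, so it needs n ≥ q + 1.

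| Metrics p | q | Minimum n | n = 5 | n = 4 |
|---|---|---|---|---|
| 2 | 4 | 5 | F(4,1), critical value 224.6 | df2 = 0, no test |
| 3 (Aim 2) | 6 | 7 | df2 = −1, no test | no test |
| 4 (Aim 1) | 8 | 9 | df2 = −3, no test | no test |

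The ranks of the error matrix on simulated data agree. For p = 2 the rank is 4 of 4 at n = 5 and 3 of 4 at n = 4. At n = 5 it is 4 of 6 for p = 3 and 4 of 8 for p = 4.

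For p = 2 and n = 5, simulated power is about 13% at a Mahalanobis distance of 2 and 29% at 5. Reaching 90% takes a distance of about 22.

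**Averaged form, participants as blocks.** Error df = (n − 1)(k − 1). Wilks' test is F on (2p, 2(error df − p + 1)). With four completers, error df = 3 × 2 = 6, which gives F(4,10) for p = 2 (critical value 3.48), F(6,8) for p = 3 and F(8,6) for p = 4. All can be computed.

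**Single contrast, enhanced versus control.** F on (p, n − p). With four completers and p = 2 this is F(2,2), critical value 19.0, which can be computed. With p = 4 and four completers df2 = 0, so it cannot.

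**Illustration of the difference.** Assume uncorrelated metrics, residual SD 1 and a linear trend totalling 2.5 SD from control to enhanced on both of two metrics. The averaged form then has about 92% power at n = 5 and 72% at n = 4. The doubly multivariate form has about 16% at n = 5. The effect size is an assumption, not a figure from the plan.

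**Chance of at least one incomplete session in five.** This is 1 − (1 − r)⁵ for an assumed per-participant rate r: 23% at r = 5%, 41% at 10%, 67% at 20%. The plan gives no rate.

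**What a mixed model recovers.** Take within-participant information only, equal residual variance σ², and no baseline covariate. Suppose one participant completes control and intermediate but misses enhanced. The variance of the enhanced-versus-control difference is:

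- five completers: 2σ²/5 = 0.40σ²;
- four completers only: 2σ²/4 = 0.50σ²;
- four completers plus the partial participant: 0.475σ².

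For the last figure, the precision linking each pair of conditions is 4/3, with 1/2 added for control–intermediate, giving 11/6. The indirect path from control to enhanced through intermediate has variance 6/11 + 3/4 = 57/44. The total is 1/(4/3 + 44/57) = 57/120 = 0.475. The share of the loss recovered is (0.50 − 0.475)/(0.50 − 0.40) = 25%.

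**Feasibility of the mixed model.** Five participants by three conditions give 15 retention values. Removing 5 for participants, 2 for conditions and 1 for the baseline slope leaves 7 residual df, or 6 if one condition is missed.

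**The case against.** The strongest reply is that the plan never names the doubly multivariate form and gives some reason to doubt it. The 90% power claim at n = 5 would need an extreme effect under that form. Challenges/Alternatives also describes a pilot MANOVA by trials per condition, which leaves a trial-level analysis open.

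A reader might infer that the planned test drops anyone who misses a condition and cannot be computed with four completers. The documents do not support that as a general statement. No passage prescribes listwise deletion, the averaged layout need not drop a partial participant, and two other forms run with four completers on two metrics. This objection stands and limits the point to one form. A trial-level analysis would still have to account for trials nested within participants, and the plan does not say that it would.

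The plan also acts on fatigue. Re-calibrating after condition 1 shortens blocks rather than emptying them, and so lowers the risk of a missed condition. That stands too, but it provides no rule for when one is missed. Extra rest also draws on a limited margin: 3 hours of data collection plus three 90-minute washouts is 7.5 of 8 hours, leaving 30 minutes for everything else (2 hours if only two washouts are needed).

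Finally, dropout is not the main trigger. With the listed metrics, the doubly multivariate test already fails with five completers. This is correct and widens the point beyond missing data.

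**Conclusion.** The concern holds for the doubly multivariate form and only there. In that form, two metrics need all five participants complete, and even then the test is F(4,1) with a critical value of 224.6; one incomplete session leaves no test. With all listed metrics it needs at least 7 (Aim 2) and 9 (Aim 1) participants, against five planned. These results follow from the plan's own counts and need no assumed effect.

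The chances of an incomplete session (23% to 67%) rest on assumed rates of 5% to 20%. The power illustration rests on an assumed effect.

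Two further inferences go beyond the documents. One is that the n = 5 power claim is wrong: without its inputs it can be neither confirmed nor refuted. The other is that losing fatigued participants biases the estimate towards fitter people: that direction is plausible, but nothing in the plan quantifies it, and in a within-subject comparison it bears mainly on generalisability.

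What remains is an unnamed form, analysis unit and metric set, and no rule for a missed condition, at a sample size where those choices decide whether a test exists. This should be settled before analysis.

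**What to change.** Replace the MANOVA sentence in section (c) with a linear mixed model for each pre-named metric, fitted to participant-level block values. Use the retention value as outcome, that block's baseline value as covariate, condition as a fixed effect, participant as a random effect, and a small-sample df method. Make enhanced versus control the primary contrast; the stated primary hypothesis does not name its comparator, so the sponsor should confirm this choice. Name one primary metric per aim, or a multiplicity rule such as Holm across the metrics. State that all completed blocks are used, including those of participants who miss a condition.

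The cost is SAP wording and standard software; the baseline blocks are already collected. There are three downsides. Missed conditions must be assumed missing at random. Separate tests replace one joint test. Recovery is limited if the enhanced condition is the one missed: a variance of 0.475σ², against 0.50σ² with four completers alone and 0.40σ² with five. The order of conditions is not stated; if the numbered order is followed, enhanced comes last.

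If the sponsor prefers to keep a MANOVA, the plan should name its form, analysis unit, metrics and handling of a missed condition, and show that the test can be computed at n = 5.

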PROTOCOL – Each trial involves: firstly, secure grasp of the cubic object placed in front of the dominant arm; secondly, pick-up the object and move towards target in front of non-dominant arm; thirdly, accurate placement onto target. The three condition groups for training task performance in Aim 1: 1) *no feedback from glove as ‘control’*, 2) *‘decay’ feedback from glove that includes audio, visual, and vibration feedback from onboard modules, and 3) enhanced feedback with the addition of mixed-mode virtual reality.* ‘Instant’ feedback is omitted given the observed improvement from baseline with ‘decay’ in persons without SCI (**Fig 4**). Enhanced feedback is ‘mixed mode’ since there still exists grasp onto a physical cubic object with the glove but interactions are viewed in VR. Subjects observe their own hand registered in VR using the LEAP® hand-tracker compatible with Oculus. The virtual cubic object is position-calibrated with the real object at the start of each trial. The glove communicates with the VR environment to cue real-time sensory feedback following detection of secure grasp. Enhanced VR feedback includes the small cubic object changing color to green and a view panel whose border also turns green. The panel also allows for posting of customized messages or images meaningful to the subject. The subject will pre-select a message, image, and sound to positively affirm achievement of secure grasp from a pool of options provided by the experimenters. Sample message and image include ‘great job’ and cartoon sunshine, respectively. At this stage, the novel VR feedback display is intended to be simple and evident ‘reward’ [44] to accelerate motor rehabilitation over the glove-only condition. **Functional performance metrics for Aim 1 include:** 1) *time to achieve secure grasp upon initial contact*, 2) *time to complete pick-up and placement of object*, 3) *motion pathlength in moving object*, 4) *error in placing object onto target*. Higher performance is indicated by reduction in these metrics.

[figure not shown]

Fig 7: Experimental protocol for enhanced training feedback condition in Aim 1. Condition includes mixed-mode feedback with manipulation of real object while observing VR environment with enhanced visual and audio feedback.

AIM 2: Investigate the effect of a “sensory” brace and virtual reality on reach performance in SCI persons with partial hand paralysis.

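### The only named test, an omnibus three-condition MANOVA, does not test the primary hypothesis about enhanced feedback, and its 90% power does not carry over to that hypothesis

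*Combined protocol and SAP*

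**What the plan says.** All of this is in section (c), Research Design and Methods, unless noted.

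- **Test:** "Repeated-measures MANOVA will be utilized given the three condition groups and two or more performance metrics specific to each aim".
- **Power:** n = 5 is called sufficient at p < 0.05 "for MANOVA across three condition groups and two performance metrics (completion time, motion pathlength) at 90% power". The basis is earlier work in able-bodied people. No effect size, SD or correlation is given.
- **Hypothesis:** the next sentence reads "The primary hypothesis for each aim is that performance after training is significantly greater with enhanced feedback". It does not say greater than what.
- **Conditions:** the analysis is to make within-subject "comparisons across three conditions: (1) control with minimal-to-no cognitive feedback, (2) intermediate level of cognitive feedback, and (3) enhanced cognitive feedback". Also: "Enhanced feedback refers to addition of VR to glove feedback in Aim 1, and addition of vibration to visual feedback in Aim 2".
- **Blocks:** each condition has a baseline block ("performing real-world task 25 times with no feedback before training"), a training block and a retention block ("performing real-world task 25 times with no feedback after training").
- **Intent in Aim 1:** under the Aim 1 protocol, the VR display is meant "to accelerate motor rehabilitation over the glove-only condition".
- **Direction:** the Aim 1 and Aim 2 protocols both treat lower metric values as better. Aim 1 lists four metrics and Aim 2 three.

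No planned contrast, follow-up test, primary metric, sidedness or multiplicity rule appears anywhere in the document.

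**The concern.** The hypothesis is directional and concerns one condition. The MANOVA asks whether the three conditions differ in any way. A significant result is consistent with enhanced feedback being best, being no better than intermediate, or being worst.

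The comparator decides what is claimed. Enhanced is built as intermediate feedback plus one element, so the new question is what that element adds. Intermediate feedback alone could separate the conditions and make the MANOVA significant. A reader could then take that result, and the 90% beside it, as support for VR or vibration. With no contrast fixed, the comparator and the metric could also be chosen after the data are seen. The section on implications for the MERIT award says these training approaches will be taken forward on further devices.

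**Working it through.** **Inputs.** From section (c): 5 participants per aim, 3 within-subject conditions, 2 metrics in the power statement, p < 0.05, 90% power. Assumed, because not stated: normal data, subject-by-condition error SD of 1 on each metric, equal effect on both metrics, and inter-metric correlation 0, 0.5 or 0.8.

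**The plan's own figure.** The 90% cannot be reproduced without an effect size. Instead, the gap between conditions was solved so that the MANOVA has 90% power, and contrasts were examined at that gap. The form of MANOVA is not stated either. The main working uses averaged Wilks, with condition tested against subject-by-condition error on (5−1)(3−1) = 8 df:

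Λ = det(E)/det(E+H), F = [(1−√Λ)/√Λ] × 7/2 on 4 and 14 df, 5% critical value Λ = 0.280. Null rejection was 5.1% in 200,000 simulated data sets.

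**Step 1: direction.** H = 5 × Σ(condition mean − grand mean)(condition mean − grand mean)′, summed over conditions. The order of conditions does not affect the sum, and reversing every sign leaves each product unchanged. E behaves the same way. So Λ is identical whichever condition is labelled enhanced and whichever direction is better. Numerically, Λ changed by less than 1e-14 in 2,000 data sets. This step needs no effect-size assumption.

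**Step 2: the contrast at 90% MANOVA power.** Each contrast is a paired t test on one metric, 4 df, two-sided 0.05, counted as a success only if the difference is a reduction. Gaps g are in error SDs. Triplets are for correlation 0 / 0.5 / 0.8.

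| True change (control, intermediate, enhanced) | g | MANOVA significant | Enhanced vs intermediate | Both contrasts succeed |
|---|---|---|---|---|
| (0, −g, −g): the added element does nothing | 2.12 / 2.59 / 2.84 | 90% | 2.5% (chance) | at most 2.5% |
| (0, −g/2, −g): equal steps | 2.46 / 3.00 / 3.29 | 90% | 32 / 44 / 51% | 30 / 43 / 50% |
| (0, 0, −g): only enhanced works | 2.12 / 2.60 / 2.85 | 90% | 71 / 86 / 91% | 55 / 77 / 85% |

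Example, equal steps at correlation 0: the paired difference has SD √2, so the standardized difference is (2.46/2)/√2 = 0.87, which gives 32%. In the same pattern enhanced versus control has 82 / 94 / 97%.

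**Step 3: sensitivity.** Rows two and three are illustrations only.
- If the effect is on the tested metric alone, success on both contrasts becomes 21–55% (row two) and 40–89% (row three).
- In the doubly multivariate form (2 contrasts × 2 metrics, F on 4 and 1 df, critical value 224.6), 90% power needs a noncentrality of about 2,430 and gaps of 19–30 SD. Contrast power in rows two and three is then about 100%. Such effects are implausible, but the plan does not exclude this form.
- Row one holds under every form, because the true increment is zero.

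**Step 4: what n = 5 gives a contrast.** Noncentral t, 4 df, noncentrality d√5: d = 1.97 gives 90% power, d = 1.68 gives 80%, d = 1.0 gives 40%. The 95% confidence interval half-width is 2.776/√5 = 1.24 SDs of the paired difference. Testing at 0.025, as in the first step of Holm over two contrasts, raises the requirement for 90% to 2.38.

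**The case against.** Four points can be made for the plan.

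1. *The comparator and direction are there to be read.* Largely right. A reader might infer that the plan has no comparator at all, and the documents do not support that: enhanced is defined as an addition to intermediate, Aim 1 sets VR against glove-only, and both aims say which way is better. But observed means show direction only. They do not show that a difference from a given comparator exceeds chance, and no test is attached to it.
2. *The 90% is already tied to the MANOVA.* Correct. A reader might infer that the plan claims 90% power for its hypothesis. It does not, though the two sentences stand together without a caution.
3. *A contrast may be well powered.* Also correct. One might infer that contrast power must fall below 90%. Steps 2 and 3 show it can exceed 90%, so only non-transfer can be claimed.
4. *This is a single-session pilot with five people per aim, and follow-up comparisons are normal practice.* The size limits the stakes, and no later decision is stated to depend on this test. Pairwise follow-ups after the MANOVA could also serve with three conditions, but none is written, and the plan itself speaks of a primary hypothesis and of significance.

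**Conclusion.** The concern holds in a limited form and should be fixed. As written, the plan does not test its primary hypothesis: the MANOVA is non-directional and does not isolate what VR or vibration adds. That conclusion is exact. At the plan's own 90%, the MANOVA would be significant in about 90% of studies in which the added element does nothing and intermediate feedback carries the effect.

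The 90% does not carry over to the hypothesis. How far contrast power differs from it cannot be settled from the documents, because the effect pattern, the correlation between metrics and the MANOVA form are all unstated. The contrast powers for equal steps and for enhanced-only effects depend on averaged Wilks and on equal effects across metrics, and should not be quoted without those conditions.

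**What to change.** Before analysis, add to the plan for each aim:

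- A paired within-subject contrast of enhanced versus intermediate on one pre-named metric, as the test of added benefit. Motion pathlength is one candidate: both aims list it and the power statement uses it. Enhanced versus control is the other planned contrast.
- Sidedness, and error control over the two contrasts by a fixed order or by Holm. Order matters. If only enhanced works, testing enhanced versus control first cuts success on the added-benefit contrast from 71 / 86 / 91% to 55 / 77 / 85% (correlation 0 / 0.5 / 0.8). Testing enhanced versus intermediate first avoids this, but if it fails, enhanced versus control cannot be claimed.
- A rule that VR or vibration is said to add benefit only if enhanced versus intermediate is significant as a reduction, with a 95% confidence interval for every contrast.
- The MANOVA as a supporting analysis, and a sentence beside the primary hypothesis saying that the 90% does not apply to it.

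Whether to analyse retention values or change from baseline, and how to adjust the remaining metrics, is the sponsor's choice, to be stated in advance.

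Cost: plan text and a less favourable power statement, with no extra enrolment or data. With 40% power at a standardized difference of 1.0, the contrast should be presented mainly as an estimate.

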PROTOCOL - The fundamental task for this aim is to reach-to-touch designated targets with a real arm (baseline, retention) or virtual arm (training). Each trial involves: firstly, moving the hand towards a specific target; secondly, minimizing pathlength of hand motion; thirdly, accurately touching the center of the target. For this Aim, prior to training across three conditions, data will be collected to train an LDA pattern classifier based on each subject's EMG patterns. This data collection involves 5 maximum isometric voluntary exertions within the brace in each of six command directions (front, back, right, left, up, and down). The three condition groups for training task performance in Aim 2: 1) no feedback and simply practicing the virtual arm task with the classifier, 2) visual feedback to control the virtual arm with complex-representative-intermittent visual feedback of a transparent guide arm to be followed, 3) visual and tactile feedback whereby vibro-tactile feedback will be added near tendon locations for muscles on the chest (pectoral), back (latissimus dorsi) and upper arm (biceps, triceps). Able-bodied subject experiments, conducted outside the scope of this proposal, will demonstrate how to provide vibration feedback that optimizes (maximizes) EMG inter-cluster distances [48] and augments isometric myoelectric control [49] with the trained classifier. Isometric training and distinct EMG activation patterns have demonstrated improved rehabilitation performance [50-52]. **Functional performance metrics for Aim 2 include:** 1) *time to touch each target*, 2) *motion pathlength of reaching arm*, 3) *contact position error from center of each target*. Higher performance is indicated by reduction in these metrics.

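### The primary hypothesis has a direction, but the only planned test is an omnibus MANOVA that ignores direction, with no contrast, lead metric or rule for metrics that disagree

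*Combined protocol and SAP*

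**What the plan says.** Section (c), Research Design and Methods, plans data analysis that "will involve *within-subject* comparisons across three conditions", with "recruitment of five participants per year" and one aim per year. The named test is: "Repeated-measures MANOVA will be utilized given the three condition groups and two or more performance metrics specific to each aim". The next sentences justify five participants from able-bodied data for "three condition groups and two performance metrics (completion time, motion pathlength) at 90% power", and state that the primary hypothesis is greater performance after training with enhanced feedback.

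Aim 1 lists four metrics: time to a secure grasp, time to pick up and place the object, path length, and placement error. Aim 2 lists three: time to touch, path length, and distance from the target centre. Both lists end with the same sentence: "Higher performance is indicated by reduction in these metrics".

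The good direction of each metric is therefore stated. The document gives no planned contrast between conditions, lead metric, hierarchy, composite, requirement that all metrics improve, univariate follow-up, or reading for a mixed result.

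**The concern.** The hypothesis has a direction and the test does not. A MANOVA asks whether the condition mean vectors differ; it does not ask whether the enhanced condition is the better one. Its p-value is the same if every difference changes sign.

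A mixed result is plausible because both aims pair time with accuracy. In Aim 2 the trial steps after moving towards the target are "secondly, minimizing pathlength of hand motion; thirdly, accurately touching the center of the target". No step asks for speed, yet time to touch is the first metric listed. A participant who slows down to be accurate follows the instructions and scores worse on time.

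Without a rule, the meaning of a significant but mixed result would be chosen after seeing data from five people.

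**Working it through.** **Inputs from the plan.** n = 5 per aim; 3 within-participant conditions; 4 metrics (Aim 1) or 3 (Aim 2); p < 0.05; 90% power claimed for two metrics.

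**Assumed, because the plan gives no effect size, SD or correlation.** Each metric shifts by d = 1.5 residual SDs in the enhanced condition only; correlations between metrics run from -0.5 to +0.5.

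**1. The plan's own figure.** The 90% power cannot be reproduced without an effect size. Solving backwards for two metrics, a participant-blocked MANOVA (Wilks, 8 error df) needs d of about 1.8 to 2.6 for correlations from -0.3 to +0.5, or 2.1 to 3.0 if the effect is graded over conditions. The fully multivariate form on 2p condition contrasts has (4, 1) df for p = 2 and needs d of about 16 to 27. It cannot be computed for 3 or 4 metrics, which need 6 or 8 contrasts from 5 participants. The blocked form is used below.

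**2. Why direction drops out.** A shift vector δ in one of three conditions has squared deviations about the mean of (4/9 + 1/9 + 1/9) = 2/3, so the noncentrality is

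λ = n × (2/3) × δ′R⁻¹δ,

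where R is the correlation matrix of the metrics. Replacing δ by -δ leaves λ unchanged, so a uniform worsening is rejected exactly as often as a uniform improvement. With four uncorrelated metrics, λ = 5 × (2/3) × 4 × 1.5² = 30 for any pattern of signs.

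**3. Why a trade-off depends on correlation.** For two metrics with correlation ρ, δ′R⁻¹δ is 2d²/(1 + ρ) if both improve and 2d²/(1 - ρ) if one improves and the other worsens equally. A one-sample Hotelling test on paired differences (n = 5, df 2 and 3) has 90% power for a joint improvement at λ = 42.9, for example d = 2.07 at ρ = 0 (5 × 2 × 2.07² ≈ 42.9). The trade-off then has λ = 42.9 × (1 + ρ)/(1 - ρ):

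| ρ | λ for trade-off | Power for trade-off |
|---|---|---|
| 0 | 42.9 | 90% |
| +0.3 | 79.6 | 99% |
| -0.3 | 23.1 | 69% |
| -0.5 | 14.3 | 50% |

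**4. Aim 1, four metrics, d = 1.5.** Simulated MANOVA rejection rates (40,000 runs per cell; rate under no effect 0.049 to 0.051; last-digit differences are simulation error):

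| Correlations | All four better | Error worse, other three better | All four worse |
|---|---|---|---|
| None | 0.58 | 0.58 | 0.58 |
| All +0.3 | 0.34 | 0.66 | 0.34 |
| All +0.5 | 0.27 | 0.78 | 0.27 |
| Error -0.3 with the rest, rest +0.5 | 0.57 | 0.31 | 0.57 |
| Error -0.5 with the rest, rest +0.5 | 0.78 | 0.27 | 0.77 |

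For Aim 2 (three metrics), all better against error worse: 0.61 and 0.62 uncorrelated; 0.42 and 0.75 with all at +0.3; 0.69 and 0.40 with error at -0.3 and the others at +0.5.

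**5. A directional composite.** Take the mean of the four standardised metrics, enhanced minus control, paired t-test, 4 df, two-sided 0.05, counted only in the good direction. With uncorrelated metrics the paired difference of the composite has SD √(2/4) = 0.707.

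- All four better: noncentrality 1.5 × √5/0.707 = 4.74, power 0.93 to 0.94.
- Error worse, other three better: mean shift (3 - 1)/4 × 1.5 = 0.75, noncentrality 2.37, favourable conclusion 0.44.
- Adding the requirement that no metric's observed mean is worse than under control: 0.91 when all four improve, about 0.01 when error worsens.
- With all correlations +0.3, the requirement moves these figures from 0.73 to 0.72 and from 0.27 to 0.01. In Aim 2 (uncorrelated) it moves them from 0.86 to 0.85 and from about 0.18 to 0.01.
- One metric alone changes: mean shift 1.5/4 = 0.375, noncentrality 1.19, power 0.15, and lower with the added requirement. That metric tested alone would have 0.44.

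**The case against.** The strongest reply is that the plan is directional where it matters. It states a directional hypothesis, gives the good direction of every metric, and never says that a significant MANOVA alone will be reported as improvement. The natural reading is a test followed by a look at the means, and the sentence on reduction can even be read as requiring every metric to fall. This stands in part: the gap is the missing contrast and conflict rule, not an absence of any direction. But an all-metrics requirement is not stated, and no test of one is planned.

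Three stronger readings are tempting, and the documents do not support them.

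- A reader might infer that a trade-off is declared significant as readily as an improvement. That holds only for uncorrelated metrics; with other correlations it is more or less readily, and none is given. Nor do the documents report such a trade-off. In the earlier able-bodied glove study, time and path length both fell, and no accuracy metric is reported.
- A reader might infer that the metrics are treated as equivalent. A MANOVA weights them through their covariance.
- A reader might infer that the endpoint changes, because sizing uses time and path length while Challenges/Alternatives cites "MANOVA significant differences in performance (pathlength and contact accuracy". The first is the basis for the sample size and the second describes a separate pilot. Neither is presented as this trial's endpoint.

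It is also fair that five participants per aim in a two-year study feeding a later proposal is a small, early investigation. That lowers the severity. It does not make an omnibus test answer a directional question.

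**Conclusion.** The concern holds in this form: the planned primary test cannot by itself support the primary hypothesis of either aim, and the plan has no stated rule for reading a mixed result. That a uniform worsening is rejected as often as a uniform improvement is exact and needs no assumption about effect size or correlation. The rejection rates are illustrations: they rest on the assumed shift of 1.5 residual SDs, on the assumed correlations, and on the participant-blocked form of the MANOVA, which the plan does not specify. The comparison of 0.91 with 0.58 also sets a focused contrast of enhanced feedback with control against an omnibus test of three conditions, so part of the gain comes from naming the contrast. This should be fixed, and it is more than a missing detail; given the study's scale it does not undermine the whole trial.

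**What to change.** In the analysis paragraph of section (c), for each aim:

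- Make the primary test a within-participant contrast of enhanced feedback against one named comparator.
- Apply it to one directional outcome: the equal-weight mean over that aim's metrics of the log-transformed or standardised block means, with lower as better. State the transformation, the standardising SD if used, and the sidedness of the test.
- Claim improvement only if this contrast favours enhanced feedback and no single metric's mean is worse than under the comparator. Fix the no-worsening limit in advance. This condition is essential: in Aim 1 two times and path length can outvote placement error, and the composite alone still favours enhanced feedback in 0.44 of such cases.
- Report each metric separately with its estimate and interval, and keep the MANOVA as supportive.

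The cost is one paragraph of wording, settled before outcome data are examined. The downside is that the weights are fixed in advance and power is low if only one metric responds. If the investigators expect that, a single lead metric with a stated no-worsening condition on error is the alternative; a lead metric alone has power 0.44 at d = 1.5 and about 0.67 at d = 2 under the same assumptions.
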